6.1 DETERMINATION OF SAMPLE SIZE

Approximately 48 patients will be enrolled in parent study GA29469, and approximately 270 patients will be enrolled in parent study GA39925. These patients will be potentially eligible for this extension study.

The purpose of this study is to evaluate the long-term safety and tolerability of efmarodocokin alfa; no formal hypothesis testing will be performed. Assumptions for sample size determination are based on a 52-week study period, in line with the study duration prior to the implementation of Protocol Version 6. Assuming approximately 50%

of patients from parent study GA39925 will enter this open-label extension study as non-responders (approximately 135 patients) and 20% of those patients will have sustained clinical remission at the end of the 52-week study period, a total of 135 evaluable patients will provide a 95% confidence interval of 13.3% to 26.7% for the point estimate of 20%. In two different 52-week maintenance Phase III studies in patients with moderate to severely active ulcerative colitis, the percentage of patients randomly assigned to the placebo arm and who had at least one serious adverse event was 6.6% (13/198) and 13.5% (37/275) respectively (Sandborn et al.; 2017; Feagan et al., 2013). Assuming a 52-week serious adverse event rate of 6.6% or 13.5% for efmarodocokin alfa in Study GA40209, 135 evaluable patients will provide a 95% confidence interval of 3% to 12% or a 95% confidence interval of 8% to 20%, respectively.

6.2 SUMMARIES OF CONDUCT OF STUDY

The numbers of patients who enroll, discontinue, or complete the study will be summarized. Reasons for premature study withdrawal will be listed and summarized. Eligibility and other major protocol deviations will be listed and evaluated for their potential effects on the interpretation of study results.

Patients who withdraw from the study, irrespective of final outcome, will be considered as non-responders at analysis. All patients who received efmarodocokin alfa in this study will be pooled for analysis. Further subgroup analysis by dose change during the study or baseline characteristics may be performed if the sample size per subgroup is sufficient.

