3.1.4.2 Definitions for Clinical Response during the Extension Study

Definitions for clinical response during the extension study are provided below for patients with UC and patients with CD. In these definitions, "baseline" refers to either the baseline score in the parent study or the last score prior to initiation of the most recent course of efmarodocokin alfa 60 μ g/kg IV Q4W during the extension study, whichever score is the most recent.

For patients with UC, clinical response during the extension study is defined as meeting one of the following:

- A \geq 3-point decrease from baseline in mMCS and a \geq 1-point decrease from baseline in Mayo rectal bleeding subscore or a Mayo rectal bleeding subscore of 0 or 1
- Achievement of clinical remission as defined in Section [3.1.4.3](#)

For patients with CD, clinical response during the extension study is defined as meeting any one of the following:

- A \geq 100-point decrease from baseline in CDAI
- For patients with a baseline CDAI of <250 : a CDAI of <150 combined with a \geq 70-point decrease from baseline in CDAI
- A \geq 50% decrease from baseline in SES-CD
- Achievement of clinical remission as defined in Section [3.1.4.3](#)

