3.1.4.3 Definitions for Clinical Remission during the Extension Study

Definitions for clinical remission during the extension study are provided below for patients with UC and patients with CD.

For patients with UC, clinical remission is defined as meeting both of the following:

- mMCS of ≤ 2
- Mayo rectal bleeding subscore of 0 and other Mayo subscores of ≤ 1

For patients with CD, clinical remission is defined as meeting one of the following:

- Patients with disease restricted to the ileum: CDAI of < 150 and SES-CD of ≤ 2
- Patients with disease not restricted to the ileum: CDAI of < 150, SES-CD of ≤ 4 , and no ulcerations

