3.1.6 Safety Follow-Up Visit and Early Termination Visit

Patients will undergo safety follow-up or early termination assessments as outlined below:

- Patients who receive at least one dose of efmarodocokin alfa must undergo safety follow-up assessments 8 weeks after their final dose of study drug.

Patients who discontinue the study prematurely (prior to Week 104) and have received at least one dose of efmarodocokin alfa should return to the clinic for an early termination visit within 1 week. Patients who discontinue prematurely without having undergone at least 8 weeks of follow-up (observation) after their final dose of efmarodocokin alfa should also return to the clinic for a safety follow-up visit 8 weeks after their final dose.

Patients who are unwilling to complete the safety follow-up visit should return to the clinic for an early termination visit no later than 30 days after their final dose.

- Patients who discontinue the study prematurely (prior to Week 104) and have not received efmarodocokin alfa should return to the clinic for an early termination visit within 30 days. Follow-up assessments are not required for patients who discontinue the study at Week 104 without having received efmarodocokin alfa.

For patients who complete Week 52 and safety follow-up assessments prior to the implementation of Protocol Version 6 and re-enter the study, safety follow-up is to be repeated for Year 2, as outlined above. Details regarding assessments at the safety follow-up visit and the early termination visit are provided in [Appendix 1](#).

Patients who permanently discontinue study drug can receive rescue therapy at the investigator's discretion.

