4.4.1 Rescue Therapy

The initiation of rescue therapy for patients with UC or CD will require permanent discontinuation of study treatment. Rescue therapy is defined as follows:

- Initiation of IV corticosteroid or rectal corticosteroid (i.e., enemas or suppositories)
- Initiation of oral corticosteroid or increase in dose of oral corticosteroid compared with baseline, with baseline defined as either the baseline dose in the parent study or the last dose prior to initiation of the most recent course of efmarodocokin alfa 60 µg/kg IV Q4W during the extension study, whichever dose is the most recent

For patients receiving ongoing concomitant oral corticosteroids upon entry into the study, the corticosteroid dose should be tapered until discontinuation as described in Section 3.1.7.

- Initiation of immunosuppressants (i.e., AZA, 6-MP, MTX, or TNF inhibitors)
- Initiation of natalizumab, etrolizumab, efalizumab, or other anti-integrin agents
- Initiation of cyclosporine, tacrolimus, sirolimus, or MMF
- Initiation of tofacitinib
- Initiation of ustekinumab

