4.6 TREATMENT, PATIENT, STUDY, AND SITE DISCONTINUATION

4.6.1 Study Treatment Discontinuation

Patients must permanently discontinue study drug if they experience any of the following:

- Any medical condition that the investigator or Sponsor determines may jeopardize the patient's safety if he or she continues to receive study drug
- Investigator or Sponsor determines it is in the best interest of the patient
- Pregnancy
- Drug-related anaphylaxis or other severe (Grade 3 or 4) drug-related hypersensitivity reaction
- Unresectable colonic mucosal dysplasia
- High-grade colonic mucosal dysplasia or colon cancer
- Requirement for rescue therapy outside defined limits of the protocol (see Section 4.4.1)
- Inability to tolerate corticosteroid taper (see Section 3.1.7)
- Disease flare (as defined in Section 3.1.4.4) while receiving efmarodocokin alfa
- Disease worsening as a result of efmarodocokin alfa treatment, in the investigator's judgment
- Malignancy or cervical Pap test with cervical intraepithelial neoplasia (CIN) of Grade >1, adenocarcinoma in situ (AIS), or high-grade squamous intraepithelial lesions (HSILs)
- De novo or reactivated serious viral infection, such as hepatitis B virus, hepatitis C virus, HIV, disseminated varicella zoster virus, or disseminated herpes simplex virus. For other serious or severe infections, see Section 5.1.2.3 and Table 4.
- Severe liver injury as defined by Hy's Law (see Section 5.3.5.7)
- *Grade 4 thromboembolism or deep vein thrombosis*

The primary reason for study treatment discontinuation should be documented on the appropriate eCRF. Patients who receive at least one dose of efmarodocokin alfa must

undergo safety follow-up assessments 8 weeks after their final dose of study drug (see Section 3.1.6 and [Appendix 1](#) for more information).

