6.5 EXPLORATORY EFFICACY ANALYSES

The analysis population for the efficacy analyses will consist of all patients.

The exploratory efficacy endpoints will be summarized by descriptive statistics based on the following calculations, with clinical response and clinical remission as defined in Sections 3.1.4.2 and 3.1.4.3.

- Proportion of patients with a clinical response
- Proportion of patients with a clinical remission
- Time from clinical remission to loss of clinical remission
- Change from baseline (i.e., either the baseline score in the parent study or the last score prior to initiation of the most recent course of efmarodocokin alfa 60 µg/kg IV Q4W during the extension study, whichever score is the most recent) in PRO2 for patients with CD

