- ^d Treatment initiation (i.e., first visit of period in which patient receives efmarodocokin alfa) may coincide with the Study Week 0 (baseline) visit or a subsequent scheduled visit that confirms the patient is not in clinical remission. The first dose of efmarodocokin alfa in the extension study is to be administered no less than 2 weeks after the last dose of study drug in parent study. For patients who complete the Week 52 visit but have not yet completed required safety assessments prior to the implementation of Protocol Version 6 (see Section 3.1.3): If treatment is resumed (*follow “Q4W When Not in Clinical Remission” column*), there must be a minimum of 2 weeks since the last dose of efmarodocokin alfa. For patients who complete the Week 52 visit and (if required) safety follow-up assessments prior to the implementation of Protocol Version 6: If the patient qualifies for study re-entry and is not in clinical remission, efmarodocokin alfa must be given within 1 week of establishing eligibility (*follow “Q4W When Not in Clinical Remission” column*).
- ^e For patients who achieve clinical remission while receiving efmarodocokin alfa, Q8W visits begin 16 weeks after *achieving clinical remission*.
- ^f Additional activities to be performed in all patients.
- ^g Patients with worsening disease, as determined by the investigator, should return to the clinic as soon as possible for a disease evaluation visit. The investigator may also schedule a disease evaluation visit to determine if a patient has achieved clinical remission. Patients who discontinue study drug prematurely (prior to Week 104) for the reasons listed in Section 4.6.1 and have received at least one dose of efmarodocokin alfa should return to the clinic for an early termination visit within 1 week of the event and will then enter the safety follow-up period. Patients who are unwilling to complete the safety follow-up period should return to the clinic for an early termination visit no later than 30 days after their final dose. Patients who discontinue the study prematurely (prior to Week 104) and have not received efmarodocokin alfa should return to the clinic for an early termination visit within 30 days. Endoscopy at the early termination visit should be conducted if the investigator deems it necessary.

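### No rule scores a non-steroid rescue agent as non-response when it is started during off-drug observation, or between Week 52 and re-entry

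*Combined protocol and SAP*

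**What the plan says.** **Scoring.** The only imputation rule is in Section 6.2: "Patients who withdraw from the study, irrespective of final outcome, will be considered as non-responders at analysis". Section 6.5 adds: "The analysis population for the efficacy analyses will consist of all patients". The definitions list score criteria and nothing else. Section 3.1.4.2 opens with "For patients with UC, clinical response during the extension study is defined as meeting one of the following" and Section 3.1.4.3 with "For patients with UC, clinical remission is defined as meeting both of the following"; the CD definitions are built the same way. None of them mentions rescue or another IBD agent.

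**Rescue.** Section 4.4.1 states: "The initiation of rescue therapy for patients with UC or CD will require permanent discontinuation of study treatment". Its list covers corticosteroids, AZA, 6-MP, MTX, TNF inhibitors, anti-integrins, cyclosporine and related agents, tofacitinib and ustekinumab. Section 4.6.1, which governs stopping study drug, has a narrower item: "Requirement for rescue therapy outside defined limits of the protocol".

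**Leaving the study.** Section 3.1.7 takes patients who need corticosteroids above their baseline dose out of the study. Appendix 1 footnote g sets an early termination visit, followed by safety follow-up, for this group: "Patients who discontinue study drug prematurely (prior to Week 104) for the reasons listed in Section 4.6.1 and have received at least one dose". Section 3.1.6 ties the same visit to a different event: "Patients who discontinue the study prematurely (prior to Week 104) and have received at least one dose of efmarodocokin alfa". For a flare off treatment, Table 2 asks only for consultation with the Medical Monitor. Rescue is not among the withdrawal reasons in Section 4.6.2, although that list is not exhaustive.

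**The concern.** Under the treat-to-remission design, patients in remission are observed without study drug, some of them for long periods. If the disease returns and the investigator starts another agent, a later remission says little about efmarodocokin alfa. Under the stated rules it still counts, provided the patient has not withdrawn and meets the scores at Week 28, 52, 80 or 104. There is no comparator arm, so nothing offsets the error, and it can only raise the reported rates. Section 1.3 says the study is to give preliminary information on whether this dosing strategy deserves Phase III study, so the descriptive rates will be read.

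**Working it through.** The plan states no figure for rescued patients, so there is none to reproduce. The check follows each rescue route through the text to see whether it ends in the Section 6.2 rule.

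1. *Corticosteroid above baseline, on or off drug.* Section 3.1.7 discontinues the patient from the study, so Section 6.2 makes the patient a non-responder. Closed.
2. *Flare or drug-related worsening while on drug.* Table 2 stops drug permanently, allows rescue and goes to safety follow-up. Footnote g adds early termination. Section 4.6.1 speaks only of drug, but exit is the natural reading. Probably closed.
3. *Off-drug observation, dosed earlier in the extension, non-steroid agent started.* Table 2 gives Medical Monitor consultation. Section 4.4.1 stops a drug the patient is not taking. Footnote g can be read to apply, because the patient has had at least one dose. Section 3.1.6 applies only once the patient leaves. Ambiguous.
4. *Off-drug observation, never dosed in the extension, non-steroid agent started.* Footnote g's drug-stopping rule requires a dose, and the matching bullet in Section 3.1.6 again presupposes leaving. Exit is not stated. These patients count only if Section 6.5 (all patients) governs rather than the sentence in Section 6.2 that pools those who received efmarodocokin alfa.
5. *Agent started after Week 52 and the required follow-up, then re-entry under Table 3.* Section 4.1.2.3 excludes users of therapies prohibited in Section 4.4.2.2, and that list does not contain TNF inhibitors, AZA, tofacitinib or ustekinumab. Section 4.1.2.2 names cyclosporine, tacrolimus, sirolimus, MMF and anti-integrins other than vedolizumab. A patient who started a TNF inhibitor in the gap is therefore not expressly excluded and, if in remission, would be observed through Week 104.

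For routes 3 to 5, footnote f applies the Week 28, 52, 80 and 104 activities to all patients. A retained patient is therefore assessed at the visits that remain, and a qualifying score is counted.

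**Size.** Let k be the number of retained rescued patients who meet the scores at a visit, and n the number analysed. The reported rate exceeds the rate with rescue scored as failure by 100 × k / n percentage points.

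- n = 320 (maximum enrolment, Section 3.1.1), k = 1: 100 × 1 / 320 = 0.31 points.
- n = 320, k = 0 (every such patient exits): 0 points.
- n = 160 (an assumption, half the maximum, since Section 3.1.1 allows for lower enrolment), k = 1: 100 × 1 / 160 = 0.63 points.

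The documents give no rescue rate, so k is unknown.

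**The case against.** The strongest reply is that most rescue is already dealt with. Steroid excess ends participation, on-drug flares go to safety follow-up, and footnote g covers dosed patients who stop for a Section 4.6.1 reason. The sentence in Section 3.1.6 allowing rescue after permanent drug discontinuation also fits care after exit. This stands. A reader might infer that rescue in general goes unscored; routes 1 and 2 show that the documents do not support that.

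Second, the never-dosed group may fall outside the pooled analysis altogether. Those patients entered in remission without extension drug, so their remission would not reflect extension treatment even without rescue. This also stands, and it leaves the previously dosed and re-entering patients as the main case. The re-entering group is limited too, because re-consent had to come within 8 weeks of implementing Version 6.

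Third, scoring rescue as failure is partly a choice of what to estimate, and Section 1.3 names combination strategies as an aim. That supports listing post-rescue scores. It does not support counting them, unmarked, in the response and remission rates.

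Finally, a reader might measure the bias against the Section 6.1 interval of 13.3% to 26.7%. That comparison does not work. The 135 patients behind it are expected non-responders, who would not be in remission and would be dosed at Week 0 (footnote c), and the interval concerns sustained remission. A patient who relapsed, was rescued and remitted again would not ordinarily count as sustained.

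**Conclusion.** The gap is real but narrow, and worth closing because it is cheap to close. It needs four things together: a non-steroid Section 4.4.1 agent started for UC or CD, during off-drug observation or between Week 52 and re-entry; a patient who is kept in or readmitted to the study; no withdrawal recorded; and qualifying scores at a scheduled visit. The direction is upward. The size cannot be determined: zero if all such patients exit, about 0.31 points for each one if 320 are analysed, and more per patient if fewer are.

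The affected rates are exploratory and descriptive, with no hypothesis test, so no power or safety conclusion changes. A reader might also infer that durability of remission needs its own rescue rule. The definitions make that unnecessary in nearly all cases, because a protocol-defined flare already means remission is lost. UC remission allows a partial Mayo score of at most 0 + 1 + 1 = 2, or 0 + 1 + 3 = 4 if the PGA is left unrestricted, against a flare minimum of 5. CD remission needs a CDAI below 150, against 220 or more for flare.

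**What to change.** **Scoring rule, Sections 6.2 and 6.5.** Score a patient as a non-responder and non-remitter at every visit after a Section 4.4.1 therapy is newly started for UC or CD, or raised above the Section 4.4.1 baseline, at any time after extension entry. Include the interval before re-entry, and apply the rule whether or not the patient stays in the study. Exclude:

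- rescue given in the parent study, since Section 4.1.1.1 admits those patients;
- use for reasons other than IBD, such as a glucocorticoid for an infusion reaction;
- corticosteroid doses already part of the Section 4.4.1 baseline.

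List scores observed after rescue separately, which serves the combination aim in Section 1.3. State also whether Section 6.2's pooled group or Section 6.5's all patients is the efficacy denominator.

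**Wording.** Align Sections 3.1.6, 3.1.7, 4.4.1, 4.6.1 and Appendix 1 footnote g on which events stop study drug and which end study participation. Who should be rescued or withdrawn remains the sponsor's decision.

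**Cost.** One scoring rule with three exclusions, and edits to existing text. Section 4.4 already records concomitant medication from entry to the final visit, and the schedule includes it at re-entry screening. The indication must be identifiable for each Section 4.4.1 agent, and start dates in the gap before re-entry must be captured. Reported response and remission rates may be slightly lower.

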6.3 SUMMARIES OF DEMOGRAPHIC AND BASELINE CHARACTERISTICS

Demographic and baseline characteristics (including age, sex, and self-reported race/ethnicity) will be summarized through use of means, standard deviations, medians, and ranges for continuous variables and proportions for categorical variables, as appropriate.

6.4 SAFETY ANALYSES

The safety analysis population will consist of all patients who received at least one dose of study drug.

The safety analysis will contribute to the evaluation of the dosing strategy in the enrolled population over the study period, the impact of total cumulative dose received in consecutive months, the impact of intermittent dosing, the impact of total amount of drug received (including dose adjustments) or total number of infusions during the study. Safety will be analyzed through descriptive summaries of adverse events, laboratory test results, and clinical data on the basis of, but not limited to, the following:

- All patients who receive at least one dose of study drug

- Total dose received overall
- Total number of infusions overall
- Total number of consecutive monthly doses
- Maximum total cumulative dose received in consecutive months

All verbatim adverse event terms will be mapped to Medical Dictionary for Regulatory Activities thesaurus terms, and adverse event severity will be graded according to NCI CTCAE v4.0.

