Grade 1	
 Continue study drug and monitor closely for worsening of symptoms.
Grade 2 or 3	
 Treat as per local standard of care. Withhold study drug until the event resolves to a Grade 1 or lower. Report event to Sponsor in an expedited manner as an AESI (see Section 5.2.3).
Grade 4	
 Permanently discontinue study drug. Notify Medical Monitor and offer medical management per local standard of care, and follow for safety. Report event to Sponsor in an expedited manner as an AESI (see Section 5.2.3).
Efmarodocokin alfa-related adverse events not described above	
Grade 1 or 2	
 Continue study drug.
Grade 3	
 Withhold study drug. If event resolves to Grade 2 or better, resume study drug at the next scheduled dose. If more than one scheduled dose will be missed because of an on-going adverse event, permanently discontinue study drug.
Grade 4	
 Permanently discontinue study drug, offer medical management per local standard of care, and follow for safety.

ADA=anti-drug antibody; AESI=adverse event of special interest; LFT=liver function test; PK=pharmacokinetic; ULN=upper limit of normal.

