5.2.2 Serious Adverse Events (Immediately Reportable to the Sponsor)

A serious adverse event is any adverse event that meets any of the following criteria:

- Is fatal (i.e., the adverse event actually causes or leads to death)
- Is life threatening (i.e., the adverse event, in the view of the investigator, places the patient at immediate risk of death)

This does not include any adverse event that, had it occurred in a more severe form or was allowed to continue, might have caused death.

- Requires or prolongs inpatient hospitalization (see Section [5.3.5.12](#))
- Results in persistent or significant disability/incapacity (i.e., the adverse event results in substantial disruption of the patient's ability to conduct normal life functions)
- Is a congenital anomaly/birth defect in a neonate/infant born to a mother exposed to study drug
- Is a significant medical event in the investigator's judgment (e.g., may jeopardize the patient or may require medical/surgical intervention to prevent one of the outcomes listed above)

The terms "severe" and "serious" are not synonymous. Severity refers to the intensity of an adverse event (e.g., rated as mild, moderate, or severe, or according to National Cancer Institute Common Terminology Criteria for Adverse Events [NCI CTCAE]; see Section 5.3.3); the event itself may be of relatively minor medical significance (such as severe headache without any further findings).

Severity and seriousness need to be independently assessed for each adverse event recorded on the eCRF.

Serious adverse events are required to be reported by the investigator to the Sponsor immediately (i.e., no more than 24 hours after learning of the event; see Section 5.4.2 for reporting instructions).

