5.2.3 Adverse Events of Special Interest (Immediately Reportable to the Sponsor)

Adverse events of special interest are required to be reported by the investigator to the Sponsor immediately (i.e., no more than 24 hours after learning of the event; see Section 5.4.2 for reporting instructions). Adverse events of special interest for this study are as follows:

- Cases of potential drug-induced liver injury that include an elevated ALT or AST in combination with either an elevated bilirubin or clinical jaundice, as defined by Hy's Law (see Section 5.3.5.7)
- Suspected transmission of an infectious agent by the study drug, as defined below
 - Any organism, virus, or infectious particle (e.g., prion protein transmitting transmissible spongiform encephalopathy), pathogenic or non-pathogenic, is considered an infectious agent. A transmission of an infectious agent may be suspected from clinical symptoms or laboratory findings that indicate an infection in a patient exposed to a medicinal product. This term applies only when a contamination of the study drug is suspected.
- Any adverse event leading to discontinuation of study drug
- New or worsening neurologic signs and symptoms that are consistent with a diagnosis of progressive multifocal leukoencephalopathy
- Suspected or confirmed COVID-19 infection
- *Grade ≥2 thromboembolism or deep vein thrombosis*

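### Section 6.4 groups safety data by end-of-study exposure totals and commits to no time at risk or time-updated exposure, so its dosing questions could show a trend with no dose effect

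*Combined protocol and SAP*

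**What the plan says.** Section 6.4 lists what the safety analysis is to help evaluate, including "the impact of total cumulative dose received in consecutive months, the impact of intermittent dosing", the total amount of drug and the number of infusions. The method is stated as "Safety will be analyzed through descriptive summaries of adverse events, laboratory test results, and clinical data on the basis of" a list of groupings. Besides all dosed patients, the groupings named are total dose, "Total number of infusions overall", the number of consecutive monthly doses, and "Maximum total cumulative dose received in consecutive months". The list is expressly not exhaustive.

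No section gives a person-time denominator, an exposure-adjusted rate, time-updated exposure or a time-to-event method for safety. Section 6.6 adds only that serum concentration will be explored against some safety endpoints.

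Other sections tie exposure to outcome and to length of capture:

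- Table 2 (Section 3.1.2) ends dosing at remission, and permanently on flare during treatment.
- Section 4.6.1: "Patients must permanently discontinue study drug if they experience any of the following", followed by a list that includes several adverse events.
- Table 4, for Grade 4 drug-related events without their own row: "Permanently discontinue study drug, offer medical management per local standard of care, and follow for safety".
- Section 5.2.3 counts as an adverse event of special interest (AESI) "Any adverse event leading to discontinuation of study drug".
- Section 5.3.1 and the adverse event footnote to Appendix 1 close reporting 8 weeks after the final dose. The Appendix 1 grid nevertheless marks adverse events at the 8-weekly off-treatment visits and at Weeks 28, 52, 80 and 104.

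**The concern.** A patient's final number of infusions is not a baseline feature. It grows with time observed, and it is cut short by the events being counted. A table of patients with an event by final exposure therefore mixes three things: any effect of dose, the length of capture, and stopping because of the event. The last two alone can produce a gradient in either direction.

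Long-term safety is the study's objective, and Section 1.3 says the study will inform Phase III dosing and safety management plans. There is no control arm against which a false gradient would stand out.

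**Working it through.** **1. The plan's own figures.** Section 6.4 states none. Those in Section 6.1 reproduce for n = 135:

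- Remission: 0.20 ± 1.96 × √(0.20 × 0.80/135) gives 13.3% to 26.7%.
- SAEs: exact (Clopper-Pearson) limits are 3.1% to 12.3% for 9/135 and 8.1% to 20.3% for 18/135, matching the stated 3% to 12% and 8% to 20%.

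These concern the whole group over 52 weeks and say nothing about summaries by exposure.

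**2. Length of capture.** In one unbroken 4-weekly course, dose n falls at week 4(n − 1), so capture ends at week 4(n − 1) + 8 = 4n + 4. With a constant hazard, no dose effect and no event that stops dosing, the proportion with an SAE is 1 − (1 − p)^((4n+4)/52), where p is the 52-week rate from Section 6.1.

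| Doses | Weeks captured | p = 6.6% | p = 13.5% |
|---|---|---|---|
| 3 | 16 | 2.1% | 4.4% |
| 7 | 32 | 4.1% | 8.5% |
| 13 | 56 | 7.1% | 14.5% |
| 26 | 108 | 13.2% | 26.0% |

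**3. Adverse events leading to discontinuation.** Each such event ends dosing, so a patient given every planned infusion cannot have one. I assumed 10% per 52 weeks on course, 25% other discontinuation per 52 weeks, 15% remission at each of Weeks 28, 52 and 80, and no dose effect. About 27% of patients with 1–3 infusions have the event, about 8% with 14–26, and none with all 26. Varying these inputs (5–15%, 10–40% and 5–30%) puts the lowest band at about 2.2 to 8 times the highest.

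**4. SAEs when some of them stop dosing.** The share that does is not given. Table 4 works mostly by grade, but its hepatic and tumor rows use laboratory thresholds or diagnoses. Table 5 requires Grade 4 and 5 events to be reported as SAEs. Against that, Section 5.2.2 says "Severity and seriousness need to be independently assessed for each adverse event recorded on the eCRF". So the share is partly constrained but cannot be derived.

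I simulated 13.5% per 52 weeks with no dose effect, up to 26 doses through Week 100, the stopping and remission rates of step 3, and capture to last dose plus 8 weeks. The bands are my own. Crude SAE proportions by final infusions:

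| Share of SAEs that stop dosing | 1–3 | 4–7 | 8–13 | 14–26 |
|---|---|---|---|---|
| None | 3% | 8% | 13% | 24% |
| A quarter | 13% | 10% | 15% | 22% |
| Half | 22% | 13% | 17% | 19% |
| Three quarters | 29% | 15% | 19% | 16% |
| All | 34% | 18% | 21% | 12% |

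**5. Do rates repair it?** The true rate is −ln(1 − 0.135) = 14.5 per 100 patient-years. Patient-years grouped by final infusions do not recover it: at half stopping they give about 106, 24, 19 and 11. Assigning each event and each week at risk to the band current at that time gives 14.2 to 14.7 in every band. Kaplan-Meier incidence with 25–75% stopping is 13.4–13.5% at Week 52 and 25.1–25.2% at Week 104, against a true 13.5% and 1 − 0.865² = 25.2%.

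**6. Sensitivity of steps 4 and 5.**

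- If patients in remission are captured to Week 104 or other discontinuation, half stopping gives about 22/21/22/19%, nearly flat, and a quarter gives 14/19/20/22%. Large gradients remain only toward the extremes of none or all stopping.
- If patients differ in underlying risk (gamma frailty, variance 1, assumed), time-updated first-event rates drift from about 14.3 to 12.0 per 100 patient-years across bands with no dose effect.
- The model gives everyone 104 weeks, but Section 3.1.3 makes Year 2 optional for some. If half stopped at Week 52 (assumed), the 14–26 band would shrink from about 51% to 25% of patients.

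**The case against.** The strongest reply is that the faulty table is not in the plan. Section 6.4 speaks of descriptive summaries that feed into an evaluation; it fixes neither proportions nor bands, and its open list leaves room for rates. No hypothesis test depends on it, Section 6.6 offers a second exposure–safety route, and the Internal Monitoring Committee reviews cumulative safety data. This stands as far as it goes: crude proportions are an inference about execution. But an open list permits a sound method without committing to one, and all four named exposure groupings are end-of-study totals.

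The second reply is that the SAE gradient depends on an unknown stopping share and on a reporting window about which the documents pull both ways. This also stands, and it removes any claim to a definite SAE trend.

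Third, the time-updated method is not free of bias, since depletion of higher-risk patients produces a mild false decline, and its bands would hold few events. That is true, but the drift in step 6 is far smaller than the distortion in patient-years by final total.

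Finally, the discontinuation example may be called a tautology. That is why a table of those events by final exposure would be uninformative about dose.

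**Conclusion.** The point holds as an omission with a demonstrated mechanism. For the dosing questions that Section 6.4 itself raises, the only groupings named can show a gradient with no dose effect, and the plan commits to nothing that would prevent it. Confidence in that is high. The rise from 4.4% to 26.0% rests on a constant hazard, one unbroken course, capture ending 8 weeks after the last dose, and no event stopping dosing. For adverse events leading to discontinuation, the link with final exposure needs no assumption; only its size does.

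A reader might infer that the sponsor will publish crude proportions, that the study will show a false cumulative-dose signal in a known direction, or that the simulated SAE percentages forecast this trial. The documents support none of these. They do not specify proportions, do not give the share of SAEs that stop dosing, and do not settle whether off-drug time after remission is captured. The SAE simulations are illustrative only. This should be fixed before analysis; it does not threaten the conduct of the trial.

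**What to change.** In Section 6.4:

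- Report SAEs, AESIs and all adverse events per 100 patient-years at risk with exact Poisson 95% intervals. Add Kaplan-Meier incidence of first SAE at Weeks 52 and 104, censored at the end of capture, with the assumption of non-informative censoring stated.
- For cumulative, consecutive and intermittent dosing, assign each event and each week at risk to the exposure band current at that time, not to the final total.
- For adverse events leading to discontinuation, count only on-course time as time at risk.
- Label any final-exposure table non-causal. State that time-updated rates remain open to confounding by disease activity, since patients not in remission receive more drug, and to depletion of higher-risk patients.

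Reconcile Section 5.3.1 and the adverse event footnote with the off-treatment adverse event visits in the Appendix 1 grid, so that time at risk is defined.

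The cost is plan wording and modest programming from dosing and event dates. The downside is imprecision. At 13.5% and under step 4's assumptions, expect about 4 to 8 SAEs per time-updated band if 135 are treated (interval about 4 to 33 per 100 patient-years in the lowest band). With 318 treated (48 + 270, an upper bound), expect about 10 to 18 (about 7 to 25).
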